Official Title: Evaluating the Effectiveness of a Food is Medicine Community Health Worker Program for Pregnant Women: Addressing Social Needs and Improving Health Outcomes

NCT#: NCT06180811

Document Date: December 29, 2023

Statistical Analysis Plan

Aim 1: To assess the feasibility of the Women's Health Delaware Food Farmacy and refine the program as needed

Descriptive statistics will be used to summarize the feasibility (i.e., acceptability, demand, and implementation; Bowen et al., 2009) of the Women's Health Delaware Food Farmacy. The feasibility will be assessed using metrics such as: (1) program satisfaction; (2) study recruitment, enrollment, and retention; (3) meals provided; (4) food consumption; (5) Community Health Worker interactions; and (6) educational videos watched. In addition, open-ended questions related to program satisfaction will be analyzed using thematic analysis.

Aim 2: To determine the prevalence of and change in social needs

Descriptive statistics will be run to summarize the number of social needs identified at baseline and postpartum and the social needs resolved and unresolved through resource referrals among patients in both the Women's Health Delaware Food Farmacy and the usual standard of care. Social needs will be identified by administering ChristianaCare's Social Determinants of Health Screener (adapted from the Accountable Health Communities Health-Related Social Needs Screening Tool; the Protocol for Responding to & Assessing Patients' Assets, Risks & Experiences Screening Tool; and the Health Leads Social Needs Screening Toolkit) and sending resource referrals on patients' behalf to support their needs, both of which are standard of care. General/generalized linear models will be run to compare changes in social needs at baseline to postpartum among all participants.

Aim 3: To evaluate the effectiveness of the Women's Health Delaware Food Farmacy on maternal and child health, healthcare utilization, and clinical event outcomes as well as patient-reported outcomes compared to the usual standard of care

A series of general/generalized linear models will be run to compare patients in the Women's Health Delaware Food Farmacy compared to the usual standard of care on a number of maternal and child health outcomes (e.g., gestational age and preeclampsia), healthcare utilization (e.g., Neonatal Intensive Care Unit admission and maternal length of stay), and clinical events (e.g., cesarean delivery and fetal death) as well as patient-reported outcomes (e.g., food security, dietary intake, quality of life, and cost-related medication underuse). Models will include indicators for randomization blocks and will also control for baseline estimates, when applicable, and relevant covariates will be considered to improve the precision of estimation of effects. In order to adjust for multiple comparisons, the Benjamini-Hochberg procedure will be used for controlling the false discovery rate (Benjamini & Hochberg, 1995). In addition, the intent-to-treat and treatment on the treated impacts will be calculated (Imbens & Angrist, 1994).

References

- Benjamini, Y., & Hochberg, Y. (1995). Controlling the false discovery rate: A practical and powerful approach to multiple testing. *Journal of the Royal Statistical Society: Series B* (*Methodological*), 57(1), 289–300. https://doi.org/10.1111/j.2517-6161.1995.tb02031.x
- Bowen, D. J., Kreuter, M., Spring, B., Cofta-Woerpel, L., Linnan, L., Weiner, D., Bakken, S., Kaplan, C. P., Squiers, L., Fabrizio, C., & Fernandez, M. (2009). How we design feasibility studies. *American Journal of Preventive Medicine*, *36*(5), 452–457. https://doi.org/10.1016/j.amepre.2009.02.002
- Imbens, G. W., & Angrist, J. D. (1994). Identification and estimation of local average treatment effects. *Econometrica*, 62(2), 467–475. https://doi.org/10.2307/2951620

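### Does the Aim 2 comparison of baseline with postpartum social needs ignore that the same women are measured twice?

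*SAP*

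**What the plan says.** The SAP section on Aim 2 has a descriptive part and one inferential sentence. The aim is "To determine the prevalence of and change in social needs". The descriptive part will "summarize the number of social needs identified at baseline and postpartum", in both the program group and usual care, together with needs resolved and unresolved after referral. The inferential sentence, which covers every participant, is: "General/generalized linear models will be run to compare changes in social needs at baseline to postpartum".

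The section does not say whether a woman contributes one row or two to these models, what distribution is used, or how the correlation between her two screeners enters the variance. Under Aim 3, which compares the arms with the same model family, the SAP adds that the models "will also control for baseline estimates, when applicable". That sentence is not repeated under Aim 2. The SAP gives no sample size, standard deviation, within-woman correlation or expected change.

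**The concern.** Two screeners from one woman are correlated, and an ordinary general or generalized linear model treats its rows as independent. The outcomes are a count of needs or the presence of each need. A Poisson or binomial model cannot take a change score that may be negative, so the generalized branch seems to lead to two rows per woman with a time term. Without a participant effect, GEE or clustered variance, the standard error of the change could then be wrong.

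With positive correlation the error is conservative: intervals too wide and real changes in social needs missed, with no excess of false positives. Women without a postpartum screener would also contribute to the baseline mean only. This is Aim 2's only inferential analysis, and different readings of the sentence could give different standard errors from the same data.

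**Working it through.** **Inputs.** From the SAP: two time points, a count of needs, the model family, and the stated purpose of comparing changes. Everything numerical below is assumed, because the SAP gives no figures: rho of 0.3, 0.5 and 0.7; SD 1.5; 100 women in total; a fall of 0.5 needs; and, for the count check, 200 women with a mean of 2 needs. There is no figure in the plan to reproduce.

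**1. Two Gaussian rows per woman treated as independent.** With equal variances and N women:

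- independent-rows SE = SD × sqrt(2/N)
- paired SE = SD × sqrt(2(1 − rho)/N)
- ratio f = 1/sqrt(1 − rho)
- actual size of a nominal 5% test = 2 × (1 − Φ(1.96 f))
- actual power where the paired test has 80% = Φ(1.96 + 0.84 − 1.96 f)

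| rho | f | actual size | actual power |
|---|---|---|---|
| 0.3 | 1.20 | 1.9% | 68% |
| 0.5 | 1.41 | 0.6% | 51% |
| 0.7 | 1.83 | 0.03% | 22% |

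**2. One worked case.** With SD 1.5, rho 0.5 and N = 100, the SEs are 1.5 × sqrt(0.02) = 0.212 and 1.5 × sqrt(0.01) = 0.150. For a fall of 0.5, paired power is Φ(0.5/0.150 − 1.96) = 92%. Using 0.212 both as the reported SE and as the true spread of the estimate gives Φ(0.5/0.212 − 1.96) = 65%. That understates the power, because the estimate still varies with SD 0.150 and only the rejection threshold is inflated, to 1.96 × 0.212 = 0.416. Actual power is Φ((0.5 − 0.416)/0.150) = 71%. On these assumptions the loss is from 92% to 71%.

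**3. One row per woman.** If the outcome is postpartum minus baseline, or postpartum adjusted for baseline, the rows are independent between women and the correlation is absorbed. Then f = 1 and nothing in steps 1 and 2 applies. Both are ordinary general or generalized linear models.

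**4. Two rows per woman with a Poisson count.** Let each woman have a gamma frailty shared by both screeners (mean 1, variance 0.5), and let counts be Poisson with mean 2 given the frailty. Then:

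- variance of a count = 2 + 2² × 0.5 = 4, so dispersion = 4/2 = 2
- covariance within a woman = 2² × 0.5 = 2, so rho = 2/4 = 0.5
- plain Poisson SE of the log rate ratio = sqrt(1/400 + 1/400) = 0.071, with 200 × 2 = 400 expected needs at each time
- dispersion-scaled SE = 0.071 × sqrt(2) = 0.100

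Here the dispersion equals 1/(1 − rho), so the overdispersion that plain Poisson ignores and the correlation that it ignores cancel. A simulation of 1,500 runs with no true change agrees:

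| Model on stacked rows | mean SE | actual size at nominal 5% |
|---|---|---|
| Plain Poisson | 0.071 | 4.7% |
| Poisson, participant-clustered variance | 0.071 | 4.9% |
| Poisson, Pearson-scaled dispersion | 0.100 | 0.5% |

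The factor of 1.41 appears only when a dispersion scale is added without a within-woman term. One change score per woman had a size of 4.3% in the same setting.

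**The case for a change.** The strongest case for a change is that the wording permits an invalid analysis and does not select a valid one. How pairing is handled is a statistical detail that belongs in a SAP, and one sentence would settle it. The Aim 3 sentence on baseline adjustment does not govern Aim 2. Baseline as a covariate also serves the contrast between arms and does not by itself test the overall change over time. A stacked binary or dispersion-scaled model would indeed be conservative.

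Most of this is correct as description. It does not show that the plan chooses a wrong analysis. Nothing in the SAP says that a woman's two screeners are to be treated as independent. Comparing changes is most naturally read as working with the change itself. The general linear branch takes a change score directly, and that label also covers repeated-measures analysis of variance, so the comparison does not require two independent rows. The missing-screener point does not separate good from bad analyses either: women with a baseline screener only also remain in a GEE or mixed model, and handling of missing data may be set out in the protocol.

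**Conclusion.** The concern does not hold as an error in the plan. Aim 2 leaves the outcome form, the distribution and the unit of analysis unwritten, and an analyst asked to compare changes in the same women would ordinarily pair the data. Only the least favourable reading, stacked rows without a within-woman term in a Gaussian, binary or dispersion-scaled model, gives the inflation of 1.20 to 1.83 for rho between 0.3 and 0.7. That reading is not what the SAP states, its error is conservative, and a plain Poisson model for counts need not show it. The sizes rest on assumed correlations, standard deviation, sample size and effect, and the Poisson result on a shared-frailty model. Writing the layout down would be a helpful clarification, but the plan need not change on this account.

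### Do the Aim 3 models understate uncertainty by ignoring that programme-arm women may share Community Health Workers?

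*SAP*

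**What the plan says.** Three places in the SAP bear on this.

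- The Official Title describes the intervention as "a Food is Medicine Community Health Worker Program for Pregnant Women".
- Aim 1 lists "Community Health Worker interactions" as one of six feasibility metrics, next to such items as meals provided and educational videos watched.
- Aim 3 names the model class, "A series of general/generalized linear models will be run to compare patients in the" programme with those under usual care, and its terms: "Models will include indicators for randomization blocks and will also control for baseline estimates, when applicable, and relevant covariates will be considered". For multiplicity, "the Benjamini-Hochberg procedure will be used for controlling the false discovery rate".

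The SAP gives no number of workers, caseload, assignment rule, sample size or intraclass correlation. It names no variance estimator for Aim 3 and excludes none. Aim 2 states that social-needs screening and the sending of referrals are standard of care and reports referral results for both arms. It does not say which staff do this work.

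**The concern.** When people deliver a treatment, patients of the same provider can have outcomes that resemble each other. Individual randomization does not prevent this, because the resemblance arises afterwards, through delivery. Ordinary linear and generalized linear models take observations as independent given the covariates, and block indicators describe the randomization, not who delivered the programme. A reader who sees a worker-delivered programme and no worker term may therefore expect standard errors that are too small for outcomes a worker could influence, such as diet, food security and quality of life. Confidence intervals would then be too narrow and p-values too small. The Benjamini-Hochberg step takes p-values as given and would not repair them, so some Aim 3 outcomes could be declared different too readily.

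**Working it through.** **Inputs.** The SAP has no figure to reproduce. Everything below is assumed: 1:1 allocation, equal total variance in the arms, two-sided 5% tests, clusters in the programme arm only, m women per worker, and intraclass correlation ICC among women with the same worker.

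**Step 1: the size if the assumptions held.** The programme-arm design effect is DE = 1 + (m − 1) × ICC. True over model standard error is r = √((1 + DE)/2). Actual type I error is 2 × (1 − Φ(1.96/r)).

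Example with m = 20 and ICC = 0.05: DE = 1 + 19 × 0.05 = 1.95; r = √(2.95/2) = 1.21; type I error = 10.7%.

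| Women per worker | ICC 0 | ICC 0.01 | ICC 0.05 |
|---|---|---|---|
| 10 | r 1.00, 5.0% | r 1.02, 5.5% | r 1.11, 7.7% |
| 20 | r 1.00, 5.0% | r 1.05, 6.1% | r 1.21, 10.7% |
| 40 | r 1.00, 5.0% | r 1.09, 7.3% | r 1.41, 16.3% |

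Simulation (20,000 trials per setting) agrees. At ICC 0, 0.01 and 0.05 the rejection rates were 5.3%, 6.5% and 10.6% with 4 workers of 20 women, 5.1%, 7.3% and 16.5% with 4 workers of 40, and 5.4%, 5.7% and 7.8% with 8 workers of 10. The arithmetic is sound. The question is whether its conditions apply to this plan.

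**Step 2: which null hypothesis.** Type I error is a statement about no effect. If the programme changes no woman's outcome, it makes no difference which worker she had, the worker-induced ICC is 0, and the first column applies: 5.0%. The other columns need workers whose effects differ, some helping and some harming, yet average exactly zero.

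**Step 3: which workers.** Those columns also treat the trial's workers as a sample from a wider population. Suppose instead that the target is the effect as delivered by the workers in this trial. With workers fixed and total variance σ², the programme-arm mean of n women has variance of about (1 − ICC)σ²/n. The model's variance estimate contains that within-worker part plus a between-worker part that cannot be negative. On average it is therefore not too small. Taking the model variance as about σ²/n per arm, the ratio of true to model standard error is √((1 − ICC + 1)/2). At ICC 0.05 that is √(1.95/2) = 0.99, so the test is, if anything, slightly conservative.

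**Step 4: whether the clustering is in one arm only.** The formula for r needs usual-care women to have no shared staff. The SAP does not say so, and Aim 2 places screening and referral in both arms. If the same staff serve both arms, or if women were already grouped before randomization (by site, for example), neither this formula nor a worker effect confined to the programme arm describes the data.

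**Step 5: which outcomes.** Social needs might seem the outcome most open to worker influence, but they are modelled under Aim 2. The false-discovery procedure is stated only under Aim 3.

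**The case for a change.** The strongest case for the concern is that the error structure of an effectiveness model belongs in the SAP, not the protocol. This SAP goes as far as naming block indicators yet is silent on the provider. A human provider is plainly part of the treatment, and it is plausible that one worker sees several women. If a reader wants to generalize to other workers, and workers really differ, intervals from the listed models would be too narrow even when the average effect is not zero. One or two sentences would settle the matter.

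Part of this stands. The mechanism is real, Benjamini-Hochberg does not correct for it, and the SAP does not say how possible clustering by worker is handled. But sharing of workers is inferred from a programme name and one feasibility metric. That the models ignore clustering is inferred from the model class and from silence about the variance estimator. Staffing and caseload are matters that an SAP commonly leaves to the protocol.

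The usual remedy is not clearly better either. With perhaps 4 to 6 workers, a random worker variance can barely be estimated, and with one or two it cannot be usefully estimated at all. Inflating the standard error by a chosen ICC replaces one assumption with another. Separate residual variances by arm have no direct counterpart for the binary outcomes in Aim 3, such as preeclampsia or cesarean delivery.

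**Conclusion.** The concern does not hold. The listed models are valid if the programme has no effect on anyone, or if the comparison concerns the programme as delivered by the workers in this trial. The illustrated inflation, up to 16.3% at 40 women per worker and ICC 0.05, needs four conditions that the SAP does not supply: shared caseloads of some size, a positive ICC, no corresponding grouping under usual care, and inference to a wider population of workers. At 10 women per worker and ICC 0.01 the type I error is 5.5%, which is negligible. For clinical outcomes such as gestational age, the ICC by worker may well be close to 0.

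Whether workers are fixed or random is a decision about the estimand on which experienced statisticians disagree, so the plan is not shown to give a wrong result. What is left is that the SAP does not mention possible clustering by worker. That is missing detail, not something the document states wrongly, contradicts or fixes badly. A protocol showing a few workers with large caseloads in the programme arm only, together with an intention to generalize beyond those workers, would reopen the question.

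### Block indicators are prescribed for every Aim 3 model; with binary outcomes, unconditional logistic regression and small blocks, odds ratios are exaggerated and type I error rises

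*SAP*

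**What the plan says.** Under Aim 3 the SAP opens with "A series of general/generalized linear models will be run to compare patients" in the Food Farmacy arm with those in usual care. It gives ten example outcomes. They include "maternal and child health outcomes (e.g., gestational age and preeclampsia"), "healthcare utilization (e.g., Neonatal Intensive Care Unit admission and maternal length of stay"), and, among clinical events, cesarean delivery and fetal death. Preeclampsia, NICU admission and cesarean delivery at least are binary.

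One adjustment rule covers the whole series: "Models will include indicators for randomization blocks and will also control for baseline estimates, when applicable". The closing qualifier most naturally belongs to the baseline values, not to the blocks. The same paragraph adds that "relevant covariates will be considered to improve the precision of estimation of effects", that "the Benjamini-Hochberg procedure will be used for controlling the false discovery rate", and that "the intent-to-treat and treatment on the treated impacts will be calculated".

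The SAP names no link function for binary outcomes, does not choose between conditional and unconditional likelihood, and does not say what the blocks are. Block size and sample size may properly be in the protocol, and their absence is not the point here.

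**The concern.** In a linear model, one indicator per block is the natural adjustment for blocked randomisation and does no harm to the treatment estimate. In an unconditional logistic model it can do harm. With small permuted blocks, each new block brings a new intercept estimated from only a few patients. At blocks of 4, a trial of 200 has 200/4 = 50 intercepts and a trial of 400 has 100. The ratio of parameters to patients never improves, so a larger trial does not remove the bias.

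Logistic regression is a common choice for a binary outcome in a generalised linear model, and permuted blocks are a common meaning of randomisation blocks. An analyst who made both choices would be following the SAP exactly. Real effects would look larger than they are, null binary outcomes would be declared significant too often, and the p-values passed to the Benjamini-Hochberg step would be too small.

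**Working it through.** **Inputs.** From the SAP: block indicators in all Aim 3 models, binary outcomes among the examples, and Benjamini-Hochberg control. The SAP gives no figure to reproduce. Assumed: 1:1 allocation balanced within blocks of size k, unconditional logit, N about 200 to 400, event risk 10-30%, a two-sided 5% level (10% also shown), and no covariates.

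**Type I error, closed form.** Take a balanced block of k patients with t events, of which a are in the treated arm. At the null the block's score is a − t/2.

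- Information used by the model after profiling out the block intercept: t(k − t)/(4k).
- True (hypergeometric) variance of the score: t(k − t)/(4(k − 1)).
- Ratio of true variance to model information: k/(k − 1), for every t and therefore for every event risk.

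The test statistic is inflated by √(k/(k − 1)), so the large-sample type I error is 2(1 − Φ(z√((k − 1)/k))). For k = 4 and z = 1.96, 1.96 × √0.75 = 1.697, which gives 9.0%.

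**Limiting odds ratio.** For each t, let α(t, β) solve (k/2)·expit(α) + (k/2)·expit(α + β) = t. The estimate tends to the β at which the average of a − (k/2)·expit(α + β) over blocks is zero. As a check, for k = 2 and t = 1, α = −β/2. The equation becomes exp(β/2) = true OR, so the limit is the OR squared: 0.50² = 0.25 and 0.70² = 0.49. The limits barely change between control risks of 10%, 20% and 30%.

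| Block size | Limit, true OR 0.50 | Limit, true OR 0.70 | Type I error, nominal 5% | Type I error, nominal 10% | Simulated Wald test, nominal 5% |
|---|---|---|---|---|---|
| 4 | 0.40 | 0.62 | 9.0% | 15.4% | 7.9-8.9% |
| 6 | 0.44 | 0.65 | 7.4% | 13.3% | 6.7-7.4% |
| 8 | 0.45 | 0.67 | 6.7% | 12.4% | 5.9-6.6% |
| 20 | 0.48 | 0.69 | 5.6% | 10.9% | 4.6-5.7% |

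The last column comes from 20,000 simulated trials per setting. With risk varying between blocks (SD 0.5 on the logit scale, N about 400), the simulated error for blocks of 4, 6 and 8 was 8.9%, 7.4% and 6.5%.

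**Second simulation.** With N of 240 and 480, control risks of 5%, 10% and 30%, and 2,000 null runs per setting, the pattern was the same. For a true OR of 0.50 the median estimate was 0.38-0.40 at blocks of 4 and 0.42-0.44 at blocks of 6. Wald type I error was 7.0-9.4% and 6.1-8.2%. Doubling N at a fixed block size did not remove the bias.

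**After Benjamini-Hochberg.** The chance of any false discovery was computed for ten independent null tests, three of them binary outcomes fitted this way:

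| Block size | 5% level | 10% level |
|---|---|---|
| 4 | 6.7-7.7% | 13.2-14.1% |
| 6 | 5.5-5.8% | 11.3-11.5% |
| 8 | 5.2-5.8% | 10.7-11.2% |

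With Mantel-Haenszel p-values in place of the logistic ones, the result for blocks of 4 to 8 was 4.6-5.0% at a 5% level and 9.2-10.1% at a 10% level.

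**Alternatives, blocks of 4 to 8, nominal 5%.** Type I error was 4.5-5.3% for block-stratified Mantel-Haenszel, 3.9-5.1% for conditional logistic regression, and 4.7-5.3% for a linear-probability model with block indicators and robust errors. At N about 400 and control risk 20%, the median conditional OR for a true 0.50 was 0.50.

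**The case against.** The strongest reply is that the SAP never mentions a logit link, odds ratios or permuted blocks. Including block terms after blocked randomisation is not wrong in itself. Whether a problem exists depends on block size, which may be in the protocol, and on a model choice that the text leaves open. The wording leans towards the harmless reading: linear models are expressly included, and the planned impacts are usually differences, which suits a linear model. This stands. The point is an open risk, not a demonstrated error.

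The bias is also specific to unconditional logit. A log-link Poisson model with complete 1:1 blocks estimates the ratio of total events in the two arms, and block intercepts do not bias it. Logistic regression without block terms also behaved acceptably in the second simulation (median OR 0.48-0.52, Wald type I error 2.8-5.8%). That simulation had no variation between blocks, however, and dropping the block terms would depart from the SAP's own rule.

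The damage to the planned error control is modest at blocks of 6, and the calculation assumes ten independent null tests although the SAP's outcome lists are only examples. That stands too. The bias in the odds ratio and the single-test error do not depend on that assumption. Finally, the qualifier in the adjustment sentence could be stretched to cover the block terms, but the SAP would still give no rule for binary outcomes.

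What does not stand is the view that this is merely an omission. The SAP gives a positive instruction, and one ordinary way of following it is invalid.

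**Conclusion.** The concern holds, conditionally. If binary Aim 3 outcomes are analysed by unconditional logistic regression with one indicator per small block, the effect is material at blocks of about 6 or fewer, slight at 8, and negligible at about 20 or more or with a few large strata. At blocks of 4 the log odds ratio is inflated by about a third (ln 0.40/ln 0.50 = 1.32), and a nominal 5% test has a large-sample error of 9.0%.

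The link, block size, sample size, event risks and false-discovery level are assumptions; the large-sample type I error does not depend on event risk. If linear models are meant, the rule is valid and the SAP only needs to say so. Confidence that the problem will arise in this trial is medium, and the change is optional but worthwhile.

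**What to change.** Keep block indicators for linear models. For binary outcomes, name one of these:

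- a linear-probability model with block indicators and robust standard errors, which the text already allows and which gives impacts as risk differences;
- conditional logistic regression stratified by block;
- a block-stratified Mantel-Haenszel analysis, if no covariates are used.

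Add that unconditional logistic regression with one indicator per small block will not be used.

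The cost is one or two sentences and standard software. Intervals widen and apparent power falls: at N = 400, control risk 20%, OR 0.50 and blocks of 4, from 78% with unconditional logit to 69-70% with the valid methods. Part of the 78% comes from the inflated test. Mantel-Haenszel cannot carry the covariates the SAP mentions; the other two can. Conditional logistic regression drops blocks in which all outcomes are the same and is slightly conservative at low risk with N = 200 (about 4%). If blocks are large, almost nothing changes.

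### Does leaving the additional Aim 3 covariates to be considered undo the false discovery rate control that the plan promises?

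*SAP*

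**What the plan says.** The paragraph under Aim 3 of the SAP opens: "A series of general/generalized linear models will be run to compare patients in the Women's Health Delaware Food Farmacy" with usual care. It names ten outcomes, all as examples. They run from gestational age, preeclampsia and neonatal intensive care admission to food security and quality of life.

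The adjustment terms come in two grades. The first is a commitment: "Models will include indicators for randomization blocks and will also control for baseline estimates, when applicable". The second is looser: "relevant covariates will be considered to improve the precision of estimation of effects". No covariate is named, no selection rule or timing is given, and nothing says whether one set serves every outcome.

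The next sentence states that "the Benjamini-Hochberg procedure will be used for controlling the false discovery rate". No false discovery rate level is given. The paragraph ends with the estimands: "the intent-to-treat and treatment on the treated impacts will be calculated".

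**The concern.** Benjamini-Hochberg takes its p-values as given. Its guarantee assumes that, when the programme has no effect on an outcome, that outcome's p-value falls below any threshold no more often than it should. If an analyst fits several covariate sets, sees the arm effect in each and keeps the most favourable one, the p-value is too small before the procedure starts, and ranking it against others does not correct it.

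The SAP puts an open modelling choice directly before a promise that depends on how the choice is made, and the choice recurs in every model of the series. At stake would be false discoveries above the intended rate, and a reader's ability to tell a planned adjusted result from a selected one.

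**Working it through.** The SAP gives no sample size, power, significance level or false discovery rate level, so there is no figure of its own to reproduce. The question is which ways of choosing covariates disturb the error rate, and by how much.

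**Procedure.** Order the m p-values and reject up to the largest i with p(i) ≤ i·q/m. With no true effects every rejection is false, so the false discovery rate equals the chance of any rejection. It should be about q.

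**Why the basis of choice matters.** Suppose covariates are chosen from data pooled over arms, and the programme affects nobody's outcome. The selection is then a function of outcomes and baseline data only. Given these, allocation is still random, so choosing in this way does not bias the test. Choice by smallest standard error does not use the size of the arm difference. Choice by smallest arm p-value uses it directly, and its p-value can never exceed that of a fixed set included in the search, so it inflates error by construction.

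**Inputs, all assumed.** Both simulations use linear models, two equal arms and q = 0.05.

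- Simulation A: ten independent null outcomes (five binary with risks of 1, 5, 10, 15 and 30%, five continuous); N = 200 or 400; four candidate covariates (2⁴ = 16 sets) explaining 10–30% of outcome variance; 4,000 trials per main setting.
- Simulation B: 10 or 20 normal outcomes; N = 80, 160 or 200; three or five candidates (2³ = 8 or 2⁵ = 32 sets) explaining 10% or 30%; 1,000–2,000 trials per setting.

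**Results with no true effects** (the per-test range for B also covers its settings with some true effects, where it refers to the null outcomes):

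| Choice of covariates | A: per test | A: any discovery | B: per test | B: any discovery |
|---|---|---|---|---|
| Full set fixed in advance | 4.6–4.8% | 4.0–4.6% | 4.8–5.3% | 4.2–6.1% |
| Smallest standard error | 4.8–5.0% | 4.2–5.4% | – | – |
| Blind to arm (covariate p < 0.10, no arm term) | – | – | 4.8–5.3% | 4.5–5.6% |
| Smallest arm p of three sets | 6.2–7.5% | 6.1–8.0% | – | – |
| Smallest arm p of all sets | 7.3–10.5% | 7.5–12.6% | 7.9–14.4% | 9–20% |

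Monte Carlo error for any discovery is roughly √(0.05 × 0.95 / trials): 0.3 points at 4,000 trials and 0.7 at 1,000.

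**Further settings.**

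- Simulation A with six candidates (2⁶ = 64 sets, 30% of variance, N = 400) and a smallest-p search gave 13.1% per test and 15.8% for any discovery.
- Simulation A with weak covariates (2% of variance, N = 400) gave at most 6.2% and 5.9%, even with the search.
- Simulation B with 3 of 10 outcomes truly affected (standardised difference 0.5, N = 160) gave a false discovery rate of 7.4–11.0% with the search, 3.4–3.6% with a fixed set and 3.2–3.6% with arm-blind choice.
- A separate run of the smallest-standard-error rule (1,500 trials per setting) gave 5.0–5.6% per test and 4.6–6.5% for any discovery. The fixed set gave 4.7–5.3% and 4.7–5.8%, with Monte Carlo error near 0.6 points on any discovery.

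**Reading this against the text.** The only purpose the SAP gives for further covariates is precision. That corresponds to the second and third rows, which stay close to nominal. The last two rows need an analyst to compare arm p-values across models, separately for each outcome, and keep the smallest.

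**The case for a change.** A purpose is not a rule. The SAP does not say that precision decides which covariates enter, or that results by arm are unseen when they are chosen. Six of the ten named outcomes (gestational age, preeclampsia, neonatal intensive care admission, maternal length of stay, cesarean delivery and fetal death) would not ordinarily have a baseline value of the same measure. For these, block indicators may be the only fixed term. Even a choice among three sets, if driven by the arm p-value, reaches 6.1–8.0%, and naming a list or rule would cost a sentence. A protocol that is not shown might contain a list, but the SAP does not refer to one.

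Most of this stands as description: the wording does not exclude a search on p-values. It does not show that the plan as written leads to one. The larger figures are upper bounds for conduct at odds with the stated aim. That inflation has the same sign in every setting adds little, since a smallest-p rule cannot give anything else.

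Nor would a covariate list settle the promise it is meant to protect. The outcome family is given only by example and the false discovery rate level is unstated. Those are separate matters, and a list for each outcome could not be completed while the set of outcomes is open.

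**Conclusion.** The concern does not call for a change. The SAP leaves the extra covariates unnamed, but it fixes the design-based terms and gives a reason for further adjustment that points away from selecting on significance. Applied for that reason, or blind to arm, the choice leaves the chance of any Benjamini-Hochberg discovery at 4.2–6.5% in all runs with no true effects, against 4.0–6.1% for a fixed set and a nominal 5%. The inflated range of about 6–20% belongs to a worst case that the text neither describes nor rules out, and it largely disappears when covariates are weak. A list or pooled-data rule would mainly write down what a careful analyst would do anyway.

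The sizes rest on assumed sample sizes, outcome numbers, covariate numbers and strengths, and a 5% level. Neither simulation specifies block or baseline terms, outcomes are independent apart from shared covariates, and only linear models were run. The figures are therefore not verified for the generalized models that the SAP also allows. The argument for arm-blind choice does not depend on the type of model.
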